**Clinical** providers may refer interested patients and document their willingness to be contacted by the study through CPRS via their progress notes and using templated language provided to them (See Appendix G). Clinicians may also send referral information via encrypted email with the same templated documentation (or comparable documentation that the Veteran is interested in hearing more about the study and gives permission for research staff to contact them). Following a chart review and preliminary phone screen to determine eligibility, potential participants will be scheduled for an initial telehealth (by video or telephone) appointment during which they will be consented to the study. Consented participants will be instructed to return the informed consent form (ICF) and Authorization for Use and Release of Individually Identifiable Health Information Collected for VHA Research (HIPAA form) to the study team using a prepaid and preaddressed envelope. Once received, a study team member will complete an assessment appointment with the participant via telehealth. After all eligibility criteria are met and the assessment is complete, if telehealth appointments are conducted via VA Video Connect (VVC) platform, participants may receive automated reminders and appointment links over email, consistent with procedures for clinical appointments using VVC. The study statistician will randomly assign eligible participants to one of the two treatment options and will notify the site study coordinator about randomization status. The site study coordinator or other appropriate research team member, will contact the participants to inform them of their group assignment. Those assigned to CABA will be contacted by their therapist and tele-or video-therapy will commence. Those assigned to TAU will be offered a referral for PTSD specialty care. The assessors will be blind to group status throughout the study whenever possible. Consistent with a national VA performance measure that requires 8 sessions to be delivered over a 14 week period, participants will be contacted by phone by a blinded assessor for the mid-treatment assessment 7 weeks after the onset of treatment. Allowing 14 weeks to complete a 10 session treatment protocol accounts for cancellations and missed sessions. Participants will then be seen for follow-up assessments 14 weeks after initiating treatment. In order to minimize drop-out and maximize retention of individuals for intent-to-treat analyses, extensive efforts will be made to stay in contact with all study participants, including individuals who drop out of treatment. CABA participants who are deemed nonresponders or relapsers (do not evidence at least a 20% reduction in PTSD or cognitive symptoms) at the post-assessment or follow-up assessment (or an increase in suicidality or substance abuse), and other participants as clinically appropriate, will be offered alternative treatment or appropriate referrals.

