## **b. Sources of Materials**

Several sources of information will serve as data for the study, including neuropsychological assessments and standardized diagnostic interviews and questionnaires administered by study personnel, audiotaped treatment sessions for individuals assigned to the CABA group (to be used for supervision, determination of adherence and competence in the intervention, achieving reliability in ratings of adherence and competence and training purposes), daily monitoring forms for individuals in the CABA group, and information from medical records. Other than the information derived from the medical records, data will be collected solely for research purposes. However, because of the clinically-relevant nature of much of this information, patients will be informed that these data may be reported in their medical record, as clinically indicated. Data will be labeled with a code number that is unique to each patient in the study. All hard copy data will be stored in locked filing cabinets in locked rooms, while all electronic data will be stored in password-protected files in a limited access folder on the secure VA network drive. Data may be temporarily stored in a locked filing cabinet at the American Lake division until it can be transported to the Seattle VA. Data will be transported between American Lake and Seattle divisions by study staff in HIPAA-compliant locked containers. Each study site will maintain a key code that links that site's patients with their coded identifier. This key code will be stored separately from all other study data and available and maintained only to the multisite co-PIs, the site PI's, the multi-site project coordinator, and the site coordinators and research assistants. Any materials with protected health information (e.g., Informed Consents) will be stored in separate locked filing cabinets from coded materials to ensure the security of patient privacy.

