## **Adequacy of Protection from Risks**

### **a. Protection Against Risk**

Trained, closely supervised staff will conduct the assessments and the intervention. Assessors conducting diagnostic psychiatric interviews will have at least one year of graduate experience or equivalent work experience, and therapists will be master's or doctoral level. Drs. [name] and [name], licensed clinical psychologists, will review weekly therapy tapes and attend to any difficulties encountered. In addition, participants will be provided with emergency contact numbers. Finally, all participants will be clearly informed of their right to withdraw at any point and Drs. [name] and [name] will recommend termination of participation (and provide appropriate referral and follow-up) if substantial decline in functioning is observed (including significant increase in alcohol or drug use). Referral will also be offered to nonresponders and any participant who requests further treatment. Specific procedures will be maintained to maximize the likelihood that participant research related material will be secure and confidential. Data will be stored in locked filing cabinets and computer databases, without names or other potentially identifiable information attached; identifiable information will be kept separately and a coding system will be used to link data and identifiers.

All SAE's, UAP's, and protocol deviations occurring at either site will be communicated to the Co-PI's immediately and necessary documentation will be submitted to the CIRB within stipulated timeframes and via designated channels in accordance with the VA Central IRB Table of Reporting Requirements.

All study personnel will follow the policies and procedures for suicide prevention and management of suicidal behavior and its aftermath anywhere within the medical center or on the premises as outlined in the VAPORHCS Medical Center Memorandum No. 11-04 and in Memorandum TX-74 for Seattle both included in the study Suicide behavior protocol, Appendix A.

**Imminent risk Protection:** The following protocol applies to participants who express indication of imminent risk or clinical emergency; this includes concerns about suicidality and homicidality.

Participants may express indicators of risk either to the study clinician or to the study assessor; the protocol differs for each of these groups and is discussed below:

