### **Standardization of intervention delivery and testing between sites**

Therapists for CABA will be PhD-level psychologists or Master’s level or greater mental health practitioners. Two therapists (one from each site) are experts in BA ([name] and [name]). Several therapists from the Portland VA and VA Puget Sound were involved in writing the CCT and CABA manuals and have experience conducting these interventions. Remaining therapists will have competence in cognitive-behavioral approaches to PTSD and/or cognitive training. All therapists will be required to complete an initial training which will involve reading the treatment manual, research protocol, and treatment related materials, reviewing therapy tapes, and, when possible, attending a half-day training with Drs. [name], [name], or [name]. If therapists have significant experience/expertise in behavioral activation and/or cognitive

rehabilitation, the half day training requirement may be waived at the discretion of the study PIs. [name] will review the session recordings of the first patient for each new therapist to ensure adherence to the treatment protocol and to provide clinical feedback when needed. Therapists are invited to participate in biweekly study phone calls to discuss clinical concerns, with more immediate consultation/supervision available with study PIs on an as needed basis.

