To assure treatment fidelity, audio recordings of sessions will be used to rate therapists on CABA treatment manual compliance. Sessions from both participating VA study sites will be digitally audio-recorded, and 20% of sessions will be randomly selected by [name], the study statistician, throughout the course of the proposed study for quality adherence and fidelity ratings. A member of the study team from the main study site (Portland VA), who will be selected and trained by the co-PIs, will serve as the adherence and fidelity rater. This rater will not be involved in delivering the treatment intervention and will be trained in adherence/fidelity coding. The rater and the Principal Investigator ([name]) will individually rate several practice tapes and any discrepancies in the practice coding will be discussed and reconciled. An adherence and fidelity instrument will be developed for use with the CABA manual (see Appendix 3 for the CCT fidelity instrument). Only when reliability has been demonstrated at 90% agreement will the rater begin independently coding treatment tapes from the proposed study. Adherence rate will be calculated as percentage of goals achieved by [name]. Audio recordings will be examined on a monthly basis. The co-PIs will meet with the therapists and other study team members on a monthly basis to discuss any discrepancies, to review any adherence/fidelity rates below 80%, and to develop a plan for ensuring that all session goals are met. If adherence and fidelity monitoring reveals that any treatment goals have not been addressed, then the therapist will be retrained on the corresponding material to properly address those inefficiencies. The therapist will be recertified prior to returning to study. If it is not possible to provide the missing information (for example, because the treatment has ended), then those subjects will be excluded from the project's dataset and statistical analyses.

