## **7.0 Privacy and Confidentiality**

This study will involve the use and collection of Protected Health Information (PHI). Multiple steps will be taken in the current investigation to protect the privacy and confidentiality of research participants. All study personnel will have current training in GCP procedures for the proper use, collection, and disclosure of PHI for research purposes. Study personnel will no longer have access to study data upon termination of employment. Per VA protocol, in the event of improper use and/or disclosure, the local ISO and Privacy Officer will be notified within one hour. A code number will be assigned to each participant and his/her information. Only the multi-site co-PI's, the local site PI's, the multi-site project coordinator, and the site coordinator will be authorized to link the code number to the participant. A Master List will be retained by the study coordinator that will allow us to match each participant's code with their information; however, this Master List will be an electronic database that is password protected, and Informed Consent Forms will be stored in a double-locked cabinet apart from participant information. We will keep participant information in a separate electronic database that is password protected.

Participants who are assigned to the CABA condition will have their therapy sessions audio-recorded using a hand held digital audio recorder. However, these digital audio files will be identified by a number assigned to the participant and will not be marked with the participant's name or other identifying information. These audio-recordings will be listened to by a member of the research staff to determine if the interventions are conducted accurately ("adherence checks"). The audio files will be uploaded into a secure, password-protected folder on the VA network. These files will not contain identifying information audio recordings of sessions will be removed directly from the audio recorders immediately following the session to encrypted,

password protected, limited access drives on the VA network. Audio recorders with session content will not leave the session room before transfer.

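### The fidelity rule deletes randomised participants from the CABA arm only, and contradicts the analysis set defined for the primary hypotheses

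*Combined protocol and SAP*

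**What the plan says.** The rule is in Section 5.5, under Standardization of intervention delivery and testing between sites. The statistician draws a random 20% of recorded sessions, which are rated against the CABA manual, and "Audio recordings will be examined on a monthly basis". A goal found unaddressed leads first to therapist retraining. The second step is the exclusion, under which the plan says "then those subjects will be excluded from the project's dataset and statistical analyses". This step depends on a condition that the plan words as "If it is not possible to provide the missing information (for example, because the treatment has ended".

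Two passages show which arm is recorded. Sources of Materials lists "audiotaped treatment sessions for individuals assigned to the CABA group", and Section 7.0 says "Participants who are assigned to the CABA condition will have their therapy sessions audio-recorded". No passage sets a fidelity rating or a matching exclusion for TAU.

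Two further reviews of recordings could bring a lapse to light. In Section 5.5 a team member "will review the session recordings of the first patient for each new therapist to ensure adherence to the treatment protocol". Under Protection Against Risk, the supervising psychologists "will review weekly therapy tapes and attend to any difficulties encountered".

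Section 5.6 (Hypotheses 1a and 1b) sets a different analysis population: all randomised participants with a baseline and at least one post-baseline evaluation. Section 5.1 (Procedures) describes efforts to stay in contact with everyone, including people who leave treatment, so as to "maximize retention of individuals for intent-to-treat analyses".

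**The concern.** Randomisation makes the two arms comparable at the start. A rule that later removes people because of something that happened during treatment, and that can operate in one arm only, undoes this. The primary comparison would set CABA participants filtered by quality of delivery against unfiltered TAU participants. A goal may go unaddressed because a session was difficult or a participant was struggling, so removal could be related to outcome. The documents neither establish nor exclude that.

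The plan also defines two analysis sets for the same hypotheses, and nothing says which prevails. An analyst would have to choose, possibly after outcomes have accrued. Because the rule removes people from the dataset as well as from the analyses, it could also prevent a later intent-to-treat check.

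**Working it through.** The plan states no figure on this point, so there is none to reproduce. The conclusion rests on the text; the arithmetic only shows scale.

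**The passages side by side**

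1. *Timing.* Treatment starts after assignment (Section 5.1), and the trigger is what was delivered in treatment. The exclusion is therefore post-randomisation.
2. *Arm.* The ratings are of compliance with the CABA manual, and therapy recordings exist for CABA only. The number of TAU participants the rule can remove is 0.
3. *Status.* Nothing labels the exclusion as a per-protocol or sensitivity set.
4. *Conflict.* Section 5.6 makes no fidelity exception and states that early terminators can be kept in the model. Given the required evaluations, someone who leaves CABA after two sessions stays in the analysis. Someone who attends all ten but whose therapist missed a goal can be deleted.

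**Inputs from the documents:** 96 per arm (Section 5.2); 10 CABA sessions (Section 5.1); 20% of sessions rated and monthly review (Section 5.5); planned effect 0.5 SD at the last time point, 15% drop-out, and alpha .04 for Hypothesis 1a (Section 5.6).

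**Assumptions:** the lapse rate q; all sessions attended; detection through the random 20% only; a 0.5 SD difference between removed and retained CABA participants.

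The random draw rates 0.20 × 960 = 192 sessions. A given participant has at least one session rated with probability 1 − 0.8^10 = 0.893.

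**(a) Every flagged lapse is beyond repair.** Here q is the share of rated sessions with an unrecoverable missed goal. The share removed is e = 1 − (1 − 0.2q)^10. If removed participants differ from retained ones by D, the full CABA mean differs from the retained mean by e × D, which is the bias. With k = 96e removed, the standard error of a simple two-group difference is multiplied by √[(1/(96 − k) + 1/96)/(2/96)].

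| q | e | removed of 96 CABA | removed of 96 TAU | bias at D = 0.5 SD | SE ratio |
|---|---|---|---|---|---|
| 2% | .039 | 3.8 | 0 | 0.02 SD | 1.010 |
| 5% | .096 | 9.2 | 0 | 0.05 SD | 1.026 |
| 10% | .183 | 17.6 | 0 | 0.09 SD | 1.054 |
| 20% | .335 | 32.2 | 0 | 0.17 SD | 1.119 |

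If lapses cluster by participant (assumed intraclass correlation 0.3), about 3, 7, 14 or 27 are removed.

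Sampling also makes removal partly arbitrary. The share of participants with any missed goal is 1 − (1 − q)^10, which is .183 at q = 2% and .893 at q = 20%. The rule would find only .039/.183 ≈ 22% of them at the lower rate and .335/.893 ≈ 38% at the higher.

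**(b) Monthly review lets earlier lapses be made good.** Here q is the rate of all lapses per session, so the series cannot be compared line by line with (a). With a review every 52/12 = 4.33 weeks at random phase, a session w weeks before the last one is unrecoverable with probability max(0, 1 − w/4.33). Summed over 10 sessions this gives 2.69 sessions at weekly spacing, or 2.06 at 1.4-week spacing (10 sessions over 14 weeks).

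| q | removed of 96 CABA | bias at D = 0.5 SD | SE increase |
|---|---|---|---|
| 5% | 2–3 | 0.01 SD | 0.5–0.7% |
| 10% | 4–5 | 0.02–0.03 SD | 1.1–1.4% |
| 20% | 8–10 | 0.04–0.05 SD | 2.2–2.8% |
| 40% | 15–19 | 0.08–0.10 SD | 4.5–6% |

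In both scenarios the bias favours CABA if those removed did worse, and goes against it if they did better.

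**Error rates.** Take 96 × 0.85 = 81.6 per arm, no true effect, and a two-sided test at .04 (sidedness is an assumption). Removing 10% of CABA at D = 0.5 SD gives a bias of 0.05 SD and an SE of √(1/81.6 + 1/73.4) = 0.161, so type I error becomes .050. Removing 20% gives a bias of 0.10 SD and type I error of .077. Power for a 0.5 SD endpoint difference at .04 falls only from .873 to .854 (10% removed) or .831 (20% removed). The main risk is bias, with loss of precision secondary.

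**The case against.** The best defence is that the rule would rarely bite. It reaches only lapses that monitoring reveals, mainly in a 20% sample, and monthly review gives a chance to supply missed content first. Scenario (b) models that process and gives clearly smaller numbers than (a). The weekly tape review is a participant-protection measure rather than a fidelity rating; if it counts, it may find lapses early enough to repair them. None of the lapse rates, the 0.5 SD difference or the clustering value comes from the documents. Lapses might cluster by therapist rather than by participant, and the simple standard error is not that of the planned mixed model. If removal is unrelated to outcome, the bias is zero.

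All of that stands as a limit on the arithmetic, and the numbers should be read only as a scale. It does not answer the textual point. Repair is possible only while treatment continues, and ended treatment is the plan's own example of when exclusion follows. The 80% adherence level in the same section prompts discussion at the monthly meeting; retraining and exclusion are triggered by any unaddressed goal. It is also fair that the retention statement in Section 5.1 concerns treatment drop-outs rather than therapist lapses. It supports the point but is not a second contradiction; the contradiction is with Section 5.6.

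**Conclusion.** The concern holds, with high confidence, and must be fixed. As written, the plan contains a post-randomisation exclusion that can occur only in the CABA arm, applies to the dataset and the statistical analyses, and contradicts the analysis set for the primary hypotheses. That conclusion needs no assumption. How many participants would be removed, and the size and direction of any bias, cannot be known from the documents. On the assumed rates, removal ranges from about 2 to 32 of 96 CABA participants, and bias from 0.01 to 0.17 SD in either direction. Bias arises only if the removed participants differ in outcome from those retained.

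**What to change.** Delete the exclusion sentence at the end of the fidelity paragraph in Section 5.5. In its place, state that fidelity ratings never remove a participant from the dataset or from the Section 5.6 analysis set, and that participants are analysed in the arm to which they were assigned. Leave the post-baseline requirement in Section 5.6 as it stands. Keep fidelity findings for therapist retraining and descriptive reporting. If an analysis restricted to adherent delivery is wanted, label it as a sensitivity analysis. Restore any participants already removed under the rule; the documents do not say whether there are any.

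The cost is a short wording change with the usual amendment approval and site notification, no new data collection, and the restoring of any deleted records. The CABA estimate may move in either direction and could be slightly less favourable.

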### **Project monitoring and oversight**

Routine communication and coordination between the study sites will primarily occur through joint teleconferenced team meetings. These meetings will be scheduled bi-weekly the first 6 months of the study and monthly the latter part of the first year, and then quarterly during years two and three. Additional meetings may occur on an as-needed basis. Some funding will be budgeted toward travel for site visits.

### **Data Collection and Instruments**

**1) Demographics and disorder/disease-related assessments.** At the assessment visit, demographic information including age, gender, ethnicity, and education will be collected. We will document severity and type of current cognitive status, PTSD symptom severity, medical and psychiatric history, current treatment, and medications. We will also collect information about any new medication changes and/or changes in additional mental health treatment at the initial and follow-up treatment visits in an effort to track any changes in the initial eligibility criteria.

**2) Measures.** The RR&D TBI RFA requires use of National Institute of Neurological Disorders and Stroke (NINDS) core Common Data Elements (CDEs) for TBI. All current (version 1) core CDE measures are included except the Cognition Subscale of the Functional Independence Measure (Cog-FIM) as the NINDS CDE website indicates that this measure is "Not sufficiently sensitive for mild TBI." Assessment measures are not limited to TBI CDEs because of the need for measures of symptoms/functional effects of

PTSD or mTBI/PTSD.

Select measures of the full testing battery will be used for telehealth administration. See below for more details:

- Clinician Administered PTSD Scale (CAPS-V). A widely used diagnostic interview, provides an overall severity score and subscale scores for symptom clusters.
- Posttraumatic Stress Disorder Checklist-Fifth Version (PCL-5). A widely used self-report measure of PTSD symptom severity.

